The rapid increase in the number of people, including SGM individuals, owning a mobile telephone has led to the development of new applications in the self-management of behavioral change interventions [17]. The proposed text-based smoking cessation intervention will include motivational messages or content specifically tailored to SGM participant characteristics to distract from cravings and will be sent based on participants' needs. While there is strong evidence that text-based tobacco cessation interventions help smokers quit smoking, no similar intervention has been conducted specifically for lesbian, gay, bisexual, and/or transgender smokers [18-20]. Reducing smoking prevalence among SGM individuals by implementing a cost-effective and tailored text-based smoking cessation intervention is a powerful cancer prevention strategy for this population.

OBJECTIVE

The objective of this study is to test the feasibility and acceptability of SmokefreeSGM, an SGM-tailored version of the SmokefreeTXT text messaging program developed by our research team.

STUDY DESIGN

We will conduct a randomized controlled trial among 100 SGM smokers living in the United States randomized to the original SmokefreeTXT program (control arm = 50) or the SmokefreeSGM program (intervention arm = 50). Data collected will be used to examine recruitment, retention, and smoking abstinence rates at 1-, 3-, and 6-months follow-up. Additionally, qualitative interviews will be conducted with 32 participants (control arm = 16, intervention arm = 16) to evaluate the acceptability of both programs among SGM smokers.

RESEARCH METHODS

Inclusion Criteria.

- 1) Age \geq 18 years
- 2) Self-identify as an LGBTQ+ individual
- 3) Currently live in the United States
- 4) Have smoked at least 100 cigarettes in their lifetime, smoke every day, and smoke \geq 5 cigarettes a day
- 5) Are willing to quit smoking in the next 15 days
- 6) Have a cell phone number with an unlimited short message service (SMS) plan
- 7) Have a positive cotinine saliva test to indicate their smoking status

Exclusion Criteria.

- 1) Have a prepaid cell phone plan (pay-as-you-go plan)
- 2) Have a cell phone number that does not work and/or is registered to someone else
- 3) Have inadequate equipment/devices (i.e., webcam, speakers, mic) for participating in telehealth sessions via Microsoft Teams, Webex, or Zoom AND cannot meet in-person

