nicotine related to cigarette smoking. It contains six questions that evaluate the quantity of cigarette consumption, the compulsion to use, and dependence. Yes/No items are scored from 0 to 1 and multiple-choice items are score from 0-3. The higher the total score, the more intense the study participant's physical dependence to nicotine. For study participants that also use electronic nicotine delivery systems (ENDS) also known as electronic cigarettes, vape pens, vapes, eHookahs, JUULS, etc; their dependence will be measured using the Penn State Electronic Cigarette Dependence Index, a 10-item scale with scores ranging from 0 to 20. The higher the total score, the more intense the study participant's dependence to ENDS.

The study participant will then set a quit date in 15 days and be enrolled in the text messaging program. Study participants will either be assigned to the control group (SmokefreeTXT) or intervention group (SmokefreeSGM) through the randomization function in REDCap. Following completion of the assessment, the study participant will be sent a \$15 e-gift card via email and mailed a 6-week supply of nicotine patches. The dosage of nicotine patches will be dependent on whether the study participant identified as a light smoker (≤ 10 cigarettes/day) or a heavy smoker (smoke > 10 cigarettes/day). Light smokers will receive 3 boxes of 14 mg nicotine patches and heavy smokers will receive 3 boxes of 21 mg nicotine patches.

1-Month Assessment

Study participants will complete the 1-month assessment (Appendix F) via phone, telehealth, or in-person and be asked a series of demographic and tobacco use questions similar to the baseline screening: changes to contact information, sexual orientation and gender identity, smoking behaviors, and nicotine patch use. The research team member will conduct a FTND and/or Penn State Electronic Cigarette Dependence Index for those study participants that have not quit smoking. The research team member will also pose the question: "As an LGBTQ+ smoker, do you feel that the content of the text messages was tailored to your needs? Can you

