Quantitative data collected via text messages will be downloaded from Mosio as an Excel, SPSS, R, SAS, or STATA dataset. These software packages will be used for analysis purposes. Study variables will be summarized using standard descriptive statistics. The distributional characteristics of relevant variables will be examined using box plots and histograms to ensure normality assumptions. Routine descriptive statistics, including proportions, means, and standard deviations as well as graphical methods will be reported to explore distributions for all variables.

Recruitment rates will be defined by dividing the number of SGM smokers who consent and complete the baseline assessment by the number of SGM smokers who are approached and invited to participate in the text-based program. Retention rates will be defined by dividing the

number of SGM smokers who remained in the text-based cessation program and completed the 3- and 6-month assessments by the number of SGM smokers recruited. The recruitment and retention rates will be calculated along with confidence intervals (CIs) for specific arms and combined arms.

We will use t-test/Mann-Whitney or chi-squared/Fisher's exact test to compare baseline demographic variables between SGM smokers and those who refuse to participate or drop out from the study. Smoking abstinence outcomes will be defined as 7-day smoking abstinence along with negative saliva cotinine tests. Because abstinence is a binary variable (yes, no) the primary method of analysis will be a simple post-test analysis among SGM smokers with a generalized logistic mixed model, using a random intercept to incorporate the intra-subject correlation. Important covariates that will be used to adjust for potential baseline differences include age, level of education, biological sex, gender identity/sexual orientation, race/ethnicity, marital status, working status, years smoking, nicotine dependence, use of other tobacco products, and living with other household members who smoke. Odds ratio (OR) of smoking abstinence in the intervention group (SmokefreeSGM) relative to the control group (SmokefreeTXT) will be used to estimate effect size. Using logistic regression, abstinence will be regressed onto a dummy coded SmokefreeSGM vs. SmokefreeTXT group indicator, with the exponentiated coefficient of the group indicator yielding the OR.

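### Effect-size odds ratio: unpenalised adjustment for 11 covariates with perhaps 10-25 abstainers, no visit named, and a 1-month abstinence rate that the described procedures cannot verify

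*Combined protocol and SAP*

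**What the plan says.** The Statistics section defines the outcome as follows: "Smoking abstinence outcomes will be defined as 7-day smoking abstinence along with negative saliva cotinine tests". It describes the primary analysis as a simple post-test comparison, to be fitted with a "generalized logistic mixed model, using a random intercept to incorporate the intra-subject correlation". On adjustment it states: "Important covariates that will be used to adjust for potential baseline differences include age, level of education, biological sex", and the list goes on to eight further variables, 11 in all. The OR of SmokefreeSGM relative to SmokefreeTXT "will be used to estimate effect size". The last sentence on the subject reads: "Using logistic regression, abstinence will be regressed onto a dummy coded SmokefreeSGM vs. SmokefreeTXT group indicator".

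No visit, visit term, covariate coding or sparse-data method is given.

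Study Design lists the follow-up times: "Data collected will be used to examine recruitment, retention, and smoking abstinence rates at 1-, 3-, and 6-months follow-up". On the 1-month visit the procedures say: "Study participants will complete the 1-month assessment (Appendix F) via phone, telehealth, or in-person". No saliva test is described there; Greater Houston residents may take an exhaled carbon monoxide test. The section on the 3- and 6-month assessments does include a saliva cotinine test.

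**The concern.** Three things do not fit together.

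- **Adjustment.** Maximum-likelihood logistic regression with about as many parameters as events gives unstable estimates that are pushed away from 1. The plan adds at least 11 covariate parameters where abstainers are likely to be few.
- **Visit.** A post-test comparison suggests one time point, but a random intercept for intra-subject correlation needs at least two. The OR sentence mentions neither a random intercept nor a visit.
- **Outcome at 1 month.** A 1-month abstinence rate is planned, but the outcome definition needs a test that is not described for that visit.

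At stake is how stable and interpretable the one effect size is that the team intends to report. The 1-Month Assessment section says a larger efficacy trial is to follow.

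**Working it through.** The plan gives no assumed abstinence rate, target OR, power or covariate coding, so there is no figure of its own to reproduce.

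**Inputs from the plan.** 50 participants per arm; 11 covariates; saliva cotinine at follow-up described at 3 and 6 months only.

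**Assumptions.** Abstinence 10-25%. Covariate parameters: 11 if each covariate takes one. With six single-parameter covariates, and education, identity/orientation, race, marital status and work at 3, 4, 4, 3 and 3 levels, the count is 6 + (2 + 3 + 3 + 2 + 2) = 18.

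**Step 1: abstainers per covariate parameter.** Abstainers per visit = 100 × rate, so 10 to 25. Lowest ratio: 10/18 = 0.6. Highest: 25/11 = 2.3.

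**Step 2: precision before any adjustment.** Take 24.6% against 15.4% at one visit with 50 per arm.
- OR = (0.246/0.754)/(0.154/0.846) = 1.8.
- SE(log OR) = √(1/12.3 + 1/37.7 + 1/7.7 + 1/42.3) = 0.51, so the 95% CI is 0.66 to 4.9.
- Risk difference = 9.2 points, ± 1.96 × √(0.246 × 0.754/50 + 0.154 × 0.846/50) = ± 15.6 points.

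**Step 3: OR from a one-visit logistic regression.** Simulated trials, true OR 1.8, Fagerström score (FTND) prognostic at log-OR -0.4 per SD, other covariates null, 1000 replicates per scenario. Entries are for 15/20/25% abstinence.

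| Fit | Median OR, 11 parameters | Median OR, 18 parameters | More than twofold off, 11 | More than twofold off, 18 |
|---|---|---|---|---|
| Full list, unpenalised | 2.04/1.96/1.97 | 2.29/2.14/2.23 | 38/32/24% | 51/42/37% |
| Full list, Firth | 1.75/1.72/1.77 | 1.70/1.73/1.82 | 26/23/16% | 27/25/19% |
| FTND only, unpenalised | not tabulated | not tabulated | 26/22/15% | 26/24/18% |

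With some omitted covariates also prognostic (16-23% abstinence), cutting the list to FTND reduced the spread of the log OR by about 20-45%. Full unpenalised adjustment moved the median OR from about 1.8-1.9 to 2.1-2.4, and Firth with the full list removed nearly all of that shift.

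**Step 4: OR from the mixed model.** Under the same conditions as the last paragraph, with two visits and random-intercept SD 2, cutting the list to FTND reduced the spread by only about 4-15%. In a separate run at SD 2 with only FTND prognostic, 95% CIs missed the true value in 4.2-7.2% of trials with the full list and 4.0-5.6% with FTND only (Monte Carlo SE about 1 point). Full adjustment is therefore tolerable in the mixed model.

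**Step 5: the 1-month outcome.** The definition requires a negative saliva cotinine test. The 1-month visit may be by phone, and its only described biochemical test is an optional carbon monoxide test for one geographic group. A 1-month rate on the stated definition cannot be obtained from these procedures.

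**The case against.** **The logistic regression sentence may only explain how the OR is read off the mixed model.** This is the natural reading. The OR is then adjusted and conditional on the participant, and by Step 4 full adjustment costs little. This stands and limits the expected gain. It does not supply a visit or visit term, or settle the 1-month outcome.

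**The trial tests feasibility.** The Objective says so: "The objective of this study is to test the feasibility and acceptability of SmokefreeSGM". No power calculation or decision rule uses the OR, and Step 2 shows it will be imprecise whatever is done. This also stands and sets the weight.

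Four stronger readings are tempting, and the documents do not support them.

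- *A reader might infer that the open wording permits clearly conflicting ORs from month 3 and month 6.* In simulation these two differ more than twofold in 20-35% of trials at random-intercept SD 2. But the same true OR was set at both visits, so that spread is sampling noise and not evidence of a harmful choice.
- *A reader might infer that the follow-on trial would be undersized.* The arithmetic is sound: a marginal OR of 1.8 at 15.4% control abstinence equals a random-intercept OR of 2.43 at SD 2 or 4.30 at SD 4. Reading these as marginal gives 119 or 40 per arm instead of 291 at 80% power. But no document says this OR will size that trial, and a planner would also have the abstinence rates.
- *A reader might infer that the mixed model should give way to GEE.* Conditional or marginal is a trade-off. The mixed model performs acceptably here, and unweighted GEE makes stronger assumptions about missing visits.
- *A reader might infer that 1-month abstinence is certainly unverified.* The 1-month form (Appendix F) is not supplied. Only the described procedures can be judged.

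**Conclusion.** The point holds in a limited form. Unpenalised adjustment for 11 covariates is a poor choice for the effect-size OR with this many participants. The harm is modest if the OR comes from the mixed model and substantial if it comes from a one-visit logistic regression, which the wording also allows. The absent visit or visit term and the mismatch over 1-month abstinence are plain from the text and rest on no assumption.

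The sizes rest on assumed abstinence rates, covariate coding, prognostic strengths and random-intercept SD, and on simulations without dropout. If abstinence is higher or the coding coarser, the gain shrinks. If participants are lost, there are fewer observed abstainers to support the same model.

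The documents do not support calling the mixed model wrong or predicting a failed later trial. This is a cheap improvement of minor to moderate weight.

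**What to change.** 1. **Adjustment.** For the effect-size OR, replace the unpenalised 11-covariate adjustment with one of two options, fixed now with its coding: a short pre-specified set (for example FTND), or Firth-penalised logistic regression with the full list at a named visit.
2. **Visit and label.** Name the visit for the OR, or keep the mixed model over 3 and 6 months with a visit term. Say whether the OR is conditional or marginal, and report a risk difference with a 95% CI beside it. The choice between mixed model and GEE is the team's.
3. **1-month abstinence.** Reconcile Study Design, the assessment procedures and Statistics, for example by labelling the 1-month rate self-reported and keeping it out of the cotinine-verified model.

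The cost is plan wording only. With a short set, chance imbalance in omitted covariates is described and not adjusted. That price looks small. With three omitted covariates made prognostic, Firth with FTND only was more than twofold off in 21/18/14% of trials, against 25/22/16% for Firth with the full list (11 parameters), and in 23/18/15% against 31/23/20% (18 parameters), at 15/20/25% abstinence. Full-list Firth keeps the team's covariates at that modest cost. A single OR over 3 and 6 months assumes the same effect at both visits.

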Cigarette smoking among sexual and gender minority (SGM) groups in the United States is higher than heterosexual and cisgender individuals [1]. The National Institutes of Health (NIH) define SGM as an umbrella term that includes individuals who identify as lesbian, gay, bisexual, asexual, transgender, Two-Spirit, queer, and/or intersex. It also includes individuals with same-sex or -gender attractions or sexual behaviors and those with a difference in sex development, as well as those whose sexual orientation, gender identity or expression, or sex development is characterized by non-binary constructs [2]. The high rate of cigarette smoking among SGM groups is attributed to several factors, including stress due to stigmatization and discrimination, as well as targeted tobacco marketing [3]. Therefore, this population is at an increased risk for developing tobacco-related health conditions such as cancer.

It has been suggested that targeted and tailored interventions could be more effective among SGM smokers because they assure a safe, validating environment that enhances receptivity to cessation [4,5]. The few reported smoking cessation interventions for SGM smokers are minimally tailored, lack a control group, lack objective verification of self-reported quit rates, and/or are based on group interventions [6-9]. Mobile health (mHealth) programs that use text messaging have been found effective for smoking cessation and other behavioral change interventions. These programs are appealing to marginalized groups who experience barriers to smoking cessation interventions and who have high rates of mobile phone and text messaging use because they allow for self-management and discretion [10-13]. Although the number of people enrolled in text messaging programs for smoking cessation is increasing, no study has

evaluated their feasibility among SGM smokers.

SmokefreeTXT is an automated, personalized, and interactive mHealth program for smoking cessation developed by the National Cancer Institute (NCI) that sends text messages 2 weeks before and up to 6 weeks after a smoker's quit date. Similar programs have been found to be effective and SmokefreeTXT has been tested among the general population as well as subgroups (i.e., pregnant smokers) [10,14-16]. However, theoretically-based smoking cessation treatments delivered via text messaging and focused on the specific needs of SGM smokers are needed.

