eligible to participate will be invited to complete Part B of the screening (through telehealth or in-person) at a later date and time where their self-reported smoking status will be verified by a saliva cotinine test. The informed consent (Appendix D) and an electronic copy of the saliva test instructions will be delivered electronically to study participants via email after they complete Part A of the screening. In an attempt to limit in-person visits, potential study participants will be mailed a saliva test kit (Alere or NICDetect) and a physical copy of the instructions in advance of their session. In-person visits will only be conducted for study participants with inadequate equipment/devices to participate in telehealth sessions. Study participants will conduct the saliva test by following the step-by-step instructions provided by the research team member. This procedure will be closely monitored by the research team member. The test results will be available when the colored band appears, which takes approximately 10 minutes.

While we are seeking to enroll 100 participants into this study, interested individuals that contact the research team after that time will be given the option to be enrolled in the SmokefreeSGM text-messaging program only. These individuals will not complete the screenings or assessments and will not be provided with nicotine patches or compensation.

Baseline Assessment

Immediately after confirming a person's eligibility to participate in the study, they will complete the Baseline Assessment (Appendix E), which will ask additional demographic and tobacco use questions: sexual orientation and gender identity, race/ethnicity, work status, marital status, number of children in household, and smoking behaviors (e.g., number of cigarettes smoked per day, past attempts to quit), among others.

Nicotine dependence will be measured using the Fagerstrom Test for Nicotine Dependence (FTND), which is a standard instrument for assessing the intensity of physical addiction to

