Once the smoking cessation intervention concludes and in order to quantitatively assess engagement, a series of 32 individual interviews will be conducted with individuals previously enrolled in the feasibility trial. In this sense, the number of text messages a participant sends, including replies to the SmokefreeTXT and SmokefreeSGM programs and keywords used, will be totaled and averages will be calculated across participants. The total will not include use of the keyword STOP, which is used for unsubscribing from the program. The percentage of

participants who use this keyword will serve as an indicator of program disengagement. We will examine means and standard deviations of numbers of text messages over the course of the 6-month program in each arm. We will use t-test/Mann-Whitney to compare the average numbers of text messages between the two arms.

Qualitative data from each individual interview will be analyzed for assessing feasibility and acceptability. Audio recordings from the 1-month assessment and individual interviews will be transcribed. Data will be analyzed by the research team using a descriptive framework approach which will allow for the exploration of a priori concepts and for new themes to emerge. Transcripts will be read and reread to gain familiarity with the subject. Analysis of the transcripts will be based on data grouping, creation of a code guide, and identification of themes from the narrative text. The coding guide will be drawn on the domains shaped by the discussion guide and themes that will emerge throughout the study. Data analysis will be performed using computer software (ATLAS.ti or NVIVO).

ETHICS

This study involves no more than minimal risk to subjects. The risk of breach of confidentiality will be addressed by indicating to study participants that their involvement and data collected from them will be kept confidential to the extent of the law, and that while the findings of the study may be published, they will not be identified. Nevertheless, this study may benefit others since this work may contribute to a greater understanding of the mechanisms underlying the acceptability of mobile health (mHealth) smoking cessation interventions among SGM groups. Results will contribute to the design of interventions targeting this underserved population of smokers.

DATA HANDLING AND RECORDING KEEPING

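### Engagement is compared between arms as a raw total of messages sent, with no denominator and an unclear programme length; a reply rate should be reported beside it

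*Combined protocol and SAP*

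**What the plan says.** The Statistics section defines the engagement variable as a count: "the number of text messages a participant sends, including replies to the SmokefreeTXT and SmokefreeSGM programs and keywords used, will be totaled". The keyword STOP is left out of the count, and the percentage of participants who use it is reported separately as a sign of disengagement. The summary is by arm: "We will examine means and standard deviations of numbers of text messages over the course of the 6-month program in each arm". The test follows: "We will use t-test/Mann-Whitney to compare the average numbers of text messages between the two arms". No significance level is given for it.

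On programme length, the Background says that SmokefreeTXT "sends text messages 2 weeks before and up to 6 weeks after a smoker's quit date". The Objective calls SmokefreeSGM a tailored version of SmokefreeTXT, but no section gives its length. On message volume, the Background says that the tailored content is intended "to distract from cravings and will be sent based on participants' needs". The two text libraries are listed as Appendix A, whose content is not in the text available for this review.

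**The concern.** A reply needs a message to reply to, so a total that includes replies reflects two things: how willing a participant is to answer, and how often the programme asks. The arms run on different libraries, and the plan neither says that the numbers of reply-inviting messages are equal nor adjusts for them. If the tailored library asks more often, SmokefreeSGM could be reported as more engaging when its participants were no readier to respond, and that reading could be carried into the design of later programmes.

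The counting period is a second problem. The Statistics section counts "over the course of the 6-month program in each arm", whereas the only schedule given for either programme is much shorter. Until the two statements are reconciled, the period that the count covers is not defined.

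**Working it through.** The plan gives no power, sample-size or significance figure for this comparison, so there is nothing of its own to reproduce.

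**Programme length.** SmokefreeTXT: 2 + 6 = 8 weeks at most (Background). Counting window: 6 months, about 26 weeks (Statistics). 8 / 26 = 0.31, so the described schedule fills about 31% of the stated window. Six months is also the time of the last follow-up assessment; no section describes a 6-month text schedule.

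**Effect of unequal prompts.** Here a prompt is a message that invites a reply.

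- From the documents: 50 participants per arm (Study Design).
- Assumed: two-sided 0.05; 30 prompts in one arm and m in the other; each participant's reply probability drawn from Beta(2,2), mean 0.5, in both arms. Willingness to reply is therefore identical by construction.

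Under this model a participant's total is beta-binomial:

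- mean = 0.5 m
- variance = m × 0.25 × (4 + m) / 5
- for m = 30: mean 15, variance 30 × 0.25 × 34 / 5 = 51

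The standard error of the difference is √((51 + variance in the other arm) / 50), and z is the difference divided by it. The approximate rejection rate is P(Z > 1.96 − z), plus a negligible opposite tail.

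| m | Difference in means | Variance | SE | z | Approximate rejection | Simulated t-test | Simulated Mann-Whitney |
|---|---|---|---|---|---|---|---|
| 33 | 1.5 | 61.05 | 1.497 | 1.00 | 17% | 16% | 15% |
| 36 | 3.0 | 72 | 1.568 | 1.91 | 48% | 47% | 41% |
| 40 | 5.0 | 88 | 1.667 | 3.00 | 85% | 85% | 78% |

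The simulations used 4,000 trials per scenario and vary by a percentage point or so between runs. With replies divided by prompts, rejection stays at about 5% for every m.

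**Sensitivity to the assumptions.** With 100 prompts in the control arm, a mean reply probability of 0.30 and beta concentration 3 (wide spread between people) or 10 (narrower), the tests on raw totals reject as follows:

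| Extra prompts in the other arm | t-test, concentration 3 / 10 | Mann-Whitney, concentration 3 / 10 |
|---|---|---|
| none | 5% / 5% | 5% / 5% |
| +10% | 9% / 16% | 8% / 14% |
| +25% | 28% / 62% | 20% / 54% |
| +50% | 71% / 99% | 51% / 96% |

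The direction is stable, but the size depends on inputs that the documents do not give. With equal prompts the raw total keeps its level.

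**What the rate cannot do.** Two checks run the other way.

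- Give both arms the same distribution of total replies but 30 against 33, 36 or 40 prompts. The per-prompt t-test then rejects in about 17%, 46% and 83% of trials, against the arm with more prompts.
- Give both arms the same prompts and reply probability, but let 10% of one arm and 40% of the other stop at a random time. Totals then reject in about 30% of trials under the Beta(2,2) model, and rates in about 5%. The rate does not register early exit.

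**The case against.** The strongest objection is that the total is a legitimate randomised comparison. Message design is part of each programme, and the number of messages a person sends under one programme or the other is a meaningful outcome. A reply rate answers a different question, misses early exit and, if messages are sent on need, divides by something that arises after randomisation. This stands, and it is why the rate should supplement the total and not replace it.

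It is also true that no section shows unequal prompt numbers. Need-based sending is mentioned for the tailored messages, but the Background also calls SmokefreeTXT personalised and interactive, so volume may vary in both arms.

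Several stronger readings are tempting, and the documents do not support them:

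- *The 6-month window biases the comparison.* It is the same for both arms. If both programmes end at 8 weeks, later weeks add little to either total. Bias would need programmes of different length.
- *Both programmes last 8 weeks.* That length is given for SmokefreeTXT only; extending it to SmokefreeSGM is inference.
- *Lower totals after STOP are an artefact.* Leaving early is partly disengagement itself, and STOP use is already reported separately.
- *Engagement is assessed only in the interviewees.* The sentence "in order to quantitatively assess engagement, a series of 32 individual interviews will be conducted" is clumsy, but Study Design and the interview procedures give the interviews to acceptability, and the counts are taken across participants in each arm.
- *Later text-only users contaminate the counts.* People who come after the 100th enrolment "will be given the option to be enrolled in the SmokefreeSGM text-messaging program only", but they are not randomised, and nothing suggests that they would be counted in an arm.

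**Conclusion.** The point holds in a limited form. The planned comparison cannot separate willingness to reply from the number of invitations to reply, and the plan contains nothing that makes those invitations equal. Whether this distorts the result depends on prompt counts that are not available. Under the assumptions above, 10% more prompts in one arm raises t-test rejection from 5% to between 9% and 16%, and 25% more to between 28% and 62%, with no difference in willingness. If the counts are equal, there is no distortion.

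The conflict over programme length is a matter of definition: the two passages must be reconciled, but a common window does not by itself create an arm difference.

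Severity is minor. General Information and Study Design base quantitative feasibility on recruitment, retention and abstinence, and engagement is not listed there.

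**What to change.** 1. State the programme length for each arm, reconcile the Statistics section with the Background, and name one common counting window for both arms.
2. For all 100 randomised participants, keep the raw total and the STOP percentage as planned.
3. Add an arm comparison of replies divided by reply-inviting messages delivered. Use Mann-Whitney on each participant's proportion, or negative binomial regression of the reply count with log(prompts delivered) as offset. Report spontaneous keyword use separately, since it answers no prompt.
4. State in advance that a difference in totals will be read as greater willingness to engage only if the reply rate agrees. Otherwise describe it as a difference in message traffic.

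The cost is a few sentences in the Statistics section and the work of flagging which messages in each library invite a reply. No new participant data are needed, provided that the vendor download includes outgoing messages; the plan does not say so, and this is assumed. Because the reply rate does not capture early exit, it must be read beside the total and the STOP percentage.
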